##### 2.2.5.4.2 Postoperative Evaluations and Data Collection

Data collected postoperatively will include:

- AP and lateral X-rays (plain films);
- VAS pain assessments (neck and arm, neck, left arm and right arm (investigational group only));
- Odom's criteria determination;
- Neurologic evaluation;
- Study-related medications;
- Length of hospital stay and
- Adverse events as defined by Section 2.2.6.1 and Section 2.2.7 of this protocol.
- [REDACTED]

#### 2.2.5.4.3 Follow-Up Evaluations and Data Collection

Follow-up evaluations at 6 weeks will include:

- AP and lateral X-rays (plain films);
- Dysphagia Handicap Index (investigational group only);
- NDI assessment;
- VAS pain assessments (neck and arm; neck, left arm and right arm (investigational group only));
- Odom's criteria determination;
- Neurologic evaluation;
- Study-related medications; and
- Adverse events as defined by Section 2.2.6.1 and Section 2.2.7 of this protocol.
- [REDACTED]

Follow-up evaluations at 3 and 6 months will include:

- AP and lateral X-rays (plain films);
- Flexion-extension X-rays (used to determine range of motion);
- Lateral bending films (starting at 6 months);
- Radiographic core lab evaluations;
- Dysphagia Handicap Index (investigational group only);
- NDI assessment;
- SF-12v2 Health Survey (6 months for investigational group only);
- VAS pain assessments (neck and arm; neck, left arm and right arm (investigational group only));
- Odom's criteria determination;
- Neurologic evaluation;
- Study-related medications;
- Work status and
- Adverse events as defined by Section 2.2.6.1 and Section 2.2.7 of this protocol.
- [REDACTED]

Follow-up evaluations at 12 and 24 months will include:

- AP and lateral X-rays (plain films);

- Flexion-extension X-rays (used to determine range of motion);
- Lateral bending films;
- MRI assessment (investigational group only at 24 month);
- Radiographic core lab evaluations;
- Dysphagia Handicap Index (investigational group only);
- NDI assessment;
- SF-12v2 Health Survey (investigational group only);
- VAS pain assessments (neck and arm; neck, left arm and right arm (investigational group only));
- Odom's Criteria determination;
- Neurologic evaluation;
- Study related medication status;
- Work status;
- Patient satisfaction assessment and
- Adverse events as defined by Section 2.2.6.1 and Section 2.2.7 of this protocol.
- [REDACTED]

Subjects who complete their 24 month visit prior to the last study subject's completion of the 24 month visit will continue to be followed annually until the last subject enrolled has completed the 24 month evaluation. However, for the purpose of primary safety and efficacy evaluations, the study completion/ termination assessment will be made at 24 months postoperatively, or at an earlier time point if the subject withdraws or is withdrawn from the study.

Follow-up evaluations annually after 24 months will include:

- AP and lateral X-rays (plain films);
- Flexion-extension X-rays (used to determine range of motion);
- Lateral bending films;
- Radiographic core lab evaluations;
- Dysphagia Handicap Index (investigational group only);
- NDI assessment;
- SF-12v2 Health Survey (investigational group only);

- VAS pain assessments (neck and arm; neck, left arm and right arm (investigational group only));
- Odom's criteria determination;
- Neurologic evaluation;
- Study related medication status;
- Work status;
- Treatment satisfaction assessment and
- Adverse events as defined by Section 2.2.6.1 and Section 2.2.7 of this protocol.
- [REDACTED]

#### 2.2.5.4.4 Radiographic Assessments

For the purposes of data capture, the following radiographic assessments will be made by two independent musculoskeletal radiologists at the core lab. A third independent radiographic reviewer will adjudicate in instances of disagreement. The radiographic assessments will include:

- Angular Motion;
- Change in Angular Motion;
- Translational Motion;
- Change in Translational Motion;
- Global Range of Motion;
- Change in Global Range of Motion;
- Disc Height;
- Change in Disc Height;
- Disc Angle;
- Change in Disc Angle;
- Spondylolisthesis;
- Change in Spondylolisthesis;
- Bridging Bone;
- Fusion Status;
- Device Condition;
- Device Subsidence;
- Device Migration;
- Device Protrusion;

- Radiolucency;
- Heterotopic Ossification;
- Osteophyte Formation;
- Endplate Sclerosis;
- Adjacent Level Disc Degeneration;
- Change in ALDD;
- Facet Degeneration;
- Stenosis;
- Modic Changes;
- Cysts and
- Additional Observations.

The in vivo endplate thickness analysis will analyze a consecutive series of the first 25 subjects with required x-rays who complete the 24 month visit and any subject with an explant and/or SAE/severe AE that is judged to be definitely-related to the device. The analysis will be performed using available x-rays from the post-operative, 12 Month, 24 Month visits and annually thereafter as set forth in the core lab protocol.

2.2.5.4.5 [REDACTED]

[REDACTED]

[REDACTED]

- [REDACTED]
- [REDACTED]
- [REDACTED]

2.2.5.4.6 Study Completion, Termination or Loss to Follow-up

Subjects are expected to remain in the study for at least 24 months following treatment. Subjects who complete their 24 month visit prior to the last study subject’s completion of the 24 month visit will continue to be followed annually until the last subject enrolled has completed the 24 month evaluation. Subjects will continue to be followed thereafter until follow-up is no longer required by

FDA. However, for the purpose of primary safety and efficacy evaluations, the study completion/termination assessment will be made at 24 months postoperatively, or at earlier time point if the subject withdraws or is withdrawn from the study.

Subjects may be withdrawn from a clinical study early due to withdrawal of Informed Consent, loss to follow-up, or Investigator medical decision. Any premature termination from the study will be documented, including the primary reason for withdrawal. In the event of a secondary index surgery requiring removal of a spinal system, every effort will be made to retrieve the explanted device for analysis. The instructions for the surgical technique for device removal of the Simplify® Disc are included in the Investigator and Study Manuals. Any subjects with a device removal of the Simplify® Disc will be followed if the subject has not withdrawn consent, in a separate cohort.

## 2.2.5.5 DATA COLLECTION SUMMARY

Time Point	Pre-op	Tx	Post-op	6 wks	3 mo	6 mo	12 mo	24 mo	Post 24 mo
Informed Consent	X								
DDD assessment (MRI, CT or X-ray)	X								
Medical History & Physical Examination	X								
DXA a	X								
AP & Lateral X-rays	X		X	X	X	X	X	X	X
Flexion & Extension X-rays	X				X	X	X	X	X
Lateral bending X-rays	X					X	X	X	X
MRI (or CT at Pre-op only) c	X							X	
Radiographic Core Lab Assessments b	X		X	X	X	X	X	X	X
Dysphagia Handicap Index	X			X	X	X	X	X	X
NDI	X			X	X	X	X	X	X
SF-12v2 Health Survey	X					X	X	X	X
VAS	X		X	X	X	X	X	X	X
Odom's Criteria			X	X	X	X	X	X	X
Neurologic Exam	X		X	X	X	X	X	X	X
Medications Taken	X		X	X	X	X	X	X	X
Work Status	X				X	X	X	X	X
Treatment Assessments		X							
Treatment Satisfaction Assessment							X	X	X
Adverse Event Assessment	N/A					As needed			
Study Completion/ Termination	N/A	N/A				As needed			

a. If indicated as described in Section 2.2.3.2 of this Protocol.    b. Made by two Core labs using radiographs.    c. CT acceptable if MRI not available at Pre-op only.

## Study windows:

1. Pre-treatment evaluations;
  - a. Radiographic studies used for verification of DDD, DEXA and baseline MRI or CT may be taken up to 6 months prior to the pre-treatment evaluation.
  - b. Flexion/extension X-rays, lateral bending and AP & lateral X-rays must be taken within 90 days of pre-treatment evaluation.
  - c. *All other pre-treatment measurements* must be done within 30 days of the pre-treatment evaluation.
  - d. *Pre-op medications* should include medications taken within 30 days prior to pre-treatment evaluation.
2. Postoperative evaluations must be taken *between 12 hours and 2 weeks* postoperatively, *except postoperative adverse events* which should be captured from the time the subject leaves the operating room up to 4 weeks postoperatively.
3. Follow-up visit evaluations will be taken at 6 weeks ( $\pm 2$  weeks), 3 months ( $\pm 2$  weeks), 6 months ( $\pm 4$  weeks), 12 months ( $\pm 2$  months), 24 months ( $\pm 2$  months) and annually thereafter. The study visit window for visits post 24 months is  $\pm 2$  months.

## 2.2.6 STATISTICAL CONSIDERATIONS

### 2.2.6.1 PRIMARY ENDPOINT

The study hypothesis is that in subjects with DDD defined as intractable radiculopathy (arm pain and/or a neurological deficit) with or without neck pain or myelopathy due to a single-level abnormality localized to the level of the disc space at one level from C3 to C7 that is unresponsive to conservative management, the Month 24 composite clinical success (CCS) rate of the Simplify® Disc will be no worse than conventional ACDF when success of ACDF is evaluated at Month 24.

- Individual success for the investigational Simplify® Disc is defined as at least a 15 point improvement in NDI Score at 24 months compared with baseline, maintenance or improvement in neurologic status at 24 months compared with baseline, no device failures or revision, reoperation, removal and/or supplemental fixation within 24 months of index procedure; and the absence of major adverse events within 24 months as defined in Section 2.2.6.1 of this protocol.
- Individual success for the control ACDF device is defined as at least a 15 point improvement in NDI Score at 24 months compared with baseline, maintenance or improvement in neurologic status at 24 months compared with baseline, no device failures or revision, reoperation, removal and/or supplemental fixation with 24 months; and the absence of major adverse events within 24 months as defined in Section 2.2.6.1 of this protocol.

Device failure is defined as breakage, migration, or mechanical failure of the components as defined in the Radiographic Evaluation Protocol.

For purpose of determining individual subject success, a major adverse event is defined as any of the following which are definitely related to the device system or to a device component as determined by the CEC:

- Permanent neurologic damage or permanent nerve root injury related to a level at or below the level treated;

- Implant or component breakage or migration that does not require revision, reoperation or removal, but causes persistent or moderate to severe dysphagia and/or
- Subject death.

Per FDA Guidance for the Preparation of IDEs for Spinal Systems, the following definitions apply:

- Reoperation - any surgical procedure at the index level that *does not involve* modification, addition or removal of any components of the device” in the postoperative or follow-up period.
- Revision - any procedure in the postoperative or follow-up period that adjusts modifies or removes part of the original implant configuration *with or without* replacement of a component – may include adjusting the position of the original configuration in the postoperative or follow-up period.
- Removal - a procedure where the entire device is removed with or without replacement of the device in the postoperative or follow-up period.
- Supplemental fixation – a procedure in which additional instrumentation not under study is implanted (e.g., supplemental placement of a rod/ screw system).

#### 2.2.6.2 STUDY SUCCESS

The null hypothesis is that the probability of achieving Month 24 composite clinical success (CCS) for patients implanted with the Simplify® Disc device is no more than 0.10 smaller than the probability of ACDF control patients achieving Month 24 CCS. This study will be considered a success if the PS-quintile adjusted, multiple imputation based, 1-sided p-value for rejecting this null hypothesis is less than 0.05.

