### 2.2.2.2 HYPOTHESIS

The study hypothesis is that in subjects with DDD defined as intractable radiculopathy (arm pain and/or a neurological deficit) with or without neck pain or myelopathy due to a single-level abnormality localized to the level of the disc space at one level from C3 to C7 that is unresponsive to conservative management, the Month 24 composite clinical success (CCS) rate of the Simplify® Disc will be no worse than conventional ACDF.

- Individual success for the investigational Simplify® Disc is defined as at least a 15 point improvement in NDI Score at 24 months compared with baseline, maintenance or improvement in neurologic status at 24 months compared with baseline, no device failures or revision, reoperation, removal and/or supplemental fixation within 24 months of index procedure; and the absence of major adverse events within 24 months as defined in Section 2.2.6.1 of this protocol.
- Individual success for the control ADCF device is defined as at least a 15 point improvement in NDI Score at 24 months compared with baseline, maintenance or improvement in neurologic status at 24 months compared with baseline, no device failures or revision, reoperation, removal and/or supplemental fixation within 24 months; and the absence of major adverse events within 24 months as defined in Section 2.2.6.1 of this protocol.

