It is assumed for the purpose of sample size analysis that at least 80% of the 116 evaluable ACDF controls, that is, N=93 will be remaining after the iterative PS sub classes determination and that the success rate will be 74.1% in the retained sample. It is possible that the effective sample size will be slightly higher since, as described below, multiple imputation will be used to address missing data from the prior study.

In order to have a sufficient size sample for safety profile evaluation, 150 investigational device patients will be enrolled. For the purpose of sample size evaluation, this value is reduced by 15% to account for loss-to-follow-up. It is further assumed that no more than 10% of the analysis set will be excluded based on design of the PS sub classes, reducing the evaluable sample size from 128 to 115.

The assumptions above imply an expected device group difference equal to equal to 7.3% for the primary endpoint. The study is designed to demonstrate non-inferiority using a non-inferiority margin equal to -10.0%.

If there were N=115 Simplify® Disc patients, then a “two-group large-sample normal approximation test of proportions with a one-sided 0.05 significance level will have 91% power to reject the null hypothesis that the test and the standard are not equivalent (the difference in proportions,  $\pi_1 - \pi_2$ , is -

0.10 or farther from zero in the same direction) in favor of the alternative hypothesis that the proportions in the two groups are equivalent, assuming that the expected difference in proportions is 0.073 and the proportion in the standard group is 0.741 [REDACTED]).

Thus, as long as the superiority margin between the Simplify® Disc and ADCF about the same as observed between Kineflex|C and ADCF, then N=115 patients included in the Simplify® Disc analysis set will result in adequate (i.e.,  $\geq 80\%$ ) statistical power. As noted above, this sample size is conservatively increased by 15% to account for potential loss-to-follow-up and by 10% to account from exclusions during the PS modeling. Therefore, the target prospective enrollment is N=150.

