#### 2.2.6.6 SUPERIORITY TESTING

If the non-inferiority study success criterion is met, superiority testing will be performed in the intent-to-treat analysis set. It will be concluded that the Simplify® Disc is superior to the ACDF control if the PS-quintile adjusted one-sided p-value determined from the multiple imputation is less than 0.05.

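### The null hypothesis in the study-success rule (section 2.2.6.2) is worded in reverse and contradicts the null behind the power calculation (section 2.2.6.4)

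*Combined protocol and SAP*

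**What the plan says.** Section 2.2.6.2 (Study Success) defines the null hypothesis for the primary comparison. It is that the probability of Month 24 composite clinical success (CCS) with the Simplify Disc "is no more than 0.10 smaller than the probability of ACDF control patients achieving Month 24 CCS". The next sentence makes the study a success if the "1-sided p-value for rejecting this null hypothesis is less than 0.05", where the p-value is adjusted for propensity-score quintile and comes from multiple imputation.

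Other sections describe the same comparison:

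- Section 2.2.6.4 (Sample Size Analysis): "The study is designed to demonstrate non-inferiority using a non-inferiority margin equal to -10.0" per cent. The power statement is the power to "reject the null hypothesis that the test and the standard are not equivalent", with the difference at minus "0.10 or farther from zero in the same direction) in favor of the alternative hypothesis that the proportions in the two groups are equivalent".
- Section 2.2.2.2 (Hypothesis): the claim is that the Month 24 CCS rate of the Simplify "Disc will be no worse than conventional ACDF". Section 2.2.6.1 (Primary Endpoint) repeats it: "Disc will be no worse than conventional ACDF when success of ACDF is evaluated at Month 24".
- Section 2.2.6.6 (Superiority Testing): "If the non-inferiority study success criterion is met, superiority testing will be performed in the intent-to-treat analysis set".

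**The concern.** A probability that is at most 0.10 below the control probability lies in the region pS − pC ≥ −0.10. That is the region a non-inferiority trial sets out to establish, so it belongs in the alternative. Section 2.2.6.2 makes it the null and then ties success to rejecting that same null. Taken at its word, the rule declares success when the device is shown to be inferior by more than the margin.

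Two things make this more than a matter of style. In the visible text, section 2.2.6.2 is the only place that ties study success to a p-value threshold for the adjusted, multiply imputed analysis; section 2.2.6.4 only justifies the sample size, using a plain two-group test. And section 2.2.6.6 opens superiority testing only when the 2.2.6.2 criterion is met, so that gate inherits the reversed wording.

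**Working it through.** **The two nulls side by side** (pS = Simplify Disc, pC = ACDF)

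| Section | Null as worded | In symbols | Rejecting it shows |
|---|---|---|---|
| 2.2.6.2 | Simplify lower by 0.10 at most | pS − pC ≥ −0.10 | Inferiority beyond the margin |
| 2.2.6.4 | Difference at −0.10 or further below | pS − pC ≤ −0.10 | Non-inferiority |

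The regions are complementary and share only the boundary at −0.10. Both cannot be the null for one comparison.

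**Inputs, all from section 2.2.6.4**

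- Simplify n = 115 (150 × 0.85 = 127.5, taken as 128; × 0.90 gives 115)
- ACDF n = 93 (0.80 × 116 = 92.8)
- pC = 0.741; expected difference d = +0.073, so pS = 0.814
- Margin 0.10; one-sided alpha 0.05, z = 1.645

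**Step 1. Reproduce the plan's power.** With unpooled variance:

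SE = √(0.814 × 0.186/115 + 0.741 × 0.259/93) = 0.0581

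Power = Φ((0.073 + 0.10)/0.0581 − 1.645) = 0.908

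A pooled variance gives 0.911. Both agree with the stated 91%, and both use the null of section 2.2.6.4.

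**Step 2. Apply each rule over a range of true differences.** For each d, pS = 0.741 + d and SE(d) = √(pS(1 − pS)/115 + 0.741 × 0.259/93).

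- Rule under the 2.2.6.4 null: P(success) = Φ((d + 0.10)/SE − 1.645)
- Literal 2.2.6.2 rule: P(success) = Φ(−1.645 − (d + 0.10)/SE)

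| True d | SE | Success, 2.2.6.4 null | Success, literal 2.2.6.2 |
|---|---|---|---|
| +0.073 | 0.0581 | 90.8% | 0.0002% |
| 0 | 0.0611 | 49.7% | 0.05% |
| −0.10 | 0.0638 | 5.0% | 5.0% |
| −0.20 | 0.0650 | 0.07% | 46% |

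**Step 3. Observed difference needed for success at SE = 0.0581**

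- 2.2.6.4 null: above −0.10 + 1.645 × 0.0581 = −0.004, about −0.4 points
- Literal 2.2.6.2: below −0.10 − 1.645 × 0.0581 = −0.196, about −19.6 points

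An observed deficit of about 20 points cannot support superiority, so under the literal rule the gate in section 2.2.6.6 would open only when superiority is out of reach.

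**The case against.** The strongest reply is that nobody would run the reversed test. Section 2.2.6.6 calls the rule a non-inferiority criterion, section 2.2.6.4 states the null correctly, sections 2.2.2.2 and 2.2.6.1 give the claim in the usual direction, and the stated power fits only that direction. On this view it is a wording correction with no effect on any result or error rate, and figures for the literal rule measure a procedure that no one plans. This stands as a statement of intent and of practical risk: the literal figures show how far apart the two texts are and do not forecast the analysis. It does not make the sentence right.

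A second reply is grammatical. The phrase could be parsed as saying that pS does not exceed the value lying 0.10 below pC, which would be the 2.2.6.4 null. That reading is strained, and a success criterion should not depend on it.

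Two limits also stand. Sections 2.2.6.9 and 2.2.6.10 are redacted, so the hypotheses may be restated there; that would not remove the conflict between 2.2.6.2 and 2.2.6.4. And the calculation uses the plan's unadjusted two-proportion approximation, so the cutoffs are illustrative for the quintile-adjusted, multiply imputed test.

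**Conclusion.** The point holds. As worded, section 2.2.6.2 puts non-inferiority in the null and gives the opposite null to section 2.2.6.4 for the same comparison. The likely cause is one reversed phrase. The contradiction is complete in direction: at the design difference the two rules give success probabilities of 90.8% and about 0.0002%. The planned test, if run as section 2.2.6.4 describes, is unaffected.

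The figures assume the plan's retained sample sizes (115 and 93), an ACDF rate of 74.1% and a normal approximation. The contradiction itself rests on the wording alone. It should be corrected because it sits in the primary decision rule, which ought to be usable without being read against its own text.

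**What to change.** Restate the null in section 2.2.6.2 to match section 2.2.6.4:

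- H0: pS − pC ≤ −0.10
- H1: pS − pC > −0.10
- Success if the one-sided p-value for rejecting H0, adjusted for propensity-score quintile and based on multiple imputation, is below 0.05. Equivalently, the lower limit of the corresponding two-sided 90% confidence interval for pS − pC lies above −0.10.

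The cost is a one-sentence wording correction. Sample size, margin, alpha, power, data collection and conduct do not change, and section 2.2.6.6 then works as written.

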#### 2.2.6.3 DESIGN OF THE OBSERVATIONAL STUDY

The 133 control subjects from the Sponsor’s prior trial will be used to form a valid control group for determining the safety and effectiveness of the Simplify® Disc device. This will be done using sub classification through propensity score (PS) quintiles (Rosenbaum and Rubin, 1983). This approach

---

 Bazaz R, Lee MJ, Yoo JU, *supra* note 13.

 Rosenbaum PR and Rubin DB. The central role of the propensity score in observational studies for causal effects. *Biometrika* 1983a, 70:41-55.

directly addresses potential selection bias inherent in non-randomized comparisons. The PS model will be evaluated according to rigorous criteria (Imbens and Rubin 2015) using a published heuristic (Maislin and Rubin 2010). Applications of this heuristic have been recently published (e.g., Keenan, Maislin, et al 2014; Arnardottir, Lim, Keenan, Maislin et al 2014; and Pak, Keenan, Jackson, Grandner, Maislin et al 2014). The heuristic is designed to identify 5 sub classes in which the groups to be compared share the same multivariate distribution of a comprehensive set of baseline variables. Within each sub class, patients are therefore equally likely to have received the Simplify® Disc or conventional ACDF. The propensity score is the observational study analogue of complete randomization in randomized experiments in the sense that its use is not intended to increase precision but only to eliminate systematic biases in treatment-control comparisons (Rubin 2008). Moreover, the "propensity score technique allows the straightforward assessment [of] whether the treatment groups overlap enough regarding baseline covariates to allow for a sensible treatment comparison" (Yue 2007).

The PS sub classes will be formed when the prospective enrollment is completed. As part of the modeling process it sometimes becomes necessary to iteratively ‘shave’ off patients from the extremes of the PS distributions in order for the Imbens and Rubin 2015 PS model estimation validity criteria to be met. Where possible, exclusions of control patients will be preferred over investigational device patients in order to maximize generalizability. Results from excluded Simplify® Disc patients will be summarized separately, compared to those in the primary analysis set,

---

